10.18 Electronic medical record

The electronic medical record will be viewed in the process of recruiting subjects and assessing compliance with in- and exclusion criteria. The subjects will have to confirm compliance with these criteria prior to starting the trial. Furthermore the medical record will be accessed to obtain pregnancy outcome.

The following data will be obtained from the subject's electronic medical record and entered in the e-CRF: Prior to enrolment:

- Record of possible ultrasound to confirm gestational age and singleton pregnancy
- Record of PUQE-24 score
- 5HT3-receptor allergy
- Pre-existing diagnosis of chronic disease

Postpartum:

- Pregnancy outcome: gestational age at birth or loss/termination of pregnancy, APGAR, gender, birth weight, placenta weight, umbilical cord pH, mode of delivery. Pregnancy outcome is a safety measure to ensure the identification of any serious adverse events.

Record of possible congenital malformations or hospitalization of the new-born at neonatal ward during the first month post-partum will be obtained from offspring's electronic medical record and entered in the e-CRF. This outcome is a safety measure to ensure the identification of any serious adverse events.

11. Assessment of Safety

Information about Adverse Events (AEs), whether reported by the subject, discovered by the investigator by reviewing diary records, detected through physical examination, laboratory test or other means, must be collected and recorded on the AE form and followed up as appropriate.

Evaluation of AEs including severity, causality, outcome and seriousness assessments must be performed by a physician.

Any AE occurring from the time the informed consent was signed by the subject and until five days after Visit 3 must be recorded and reported on an AE page in the e-CRF.

Standardised report forms for AEs and SAEs will be provided as part of the e-CRF.

11.1 Definitions – Adverse Event (AE)

An AE is any untoward medical occurrence in a subject administered a medicinal product/device even if it does not necessarily have a causal relationship with this treatment.

The following events should not be recorded as AEs:

- A pre-planned procedure, e.g. a surgical intervention, unless the condition for which the procedure was planned has worsened since the informed consent form was signed.
- Pre-existing conditions documented as medical history. Any worsening in severity or frequency of a pre-existing condition during the clinical trial period must be regarded as an AE.

11.2 Definitions – Serious Adverse Event (SAE) / Serious Adverse Reaction (SAR)

A serious adverse event/reaction is an experience that at any dose results in any of the following:

- Results in death
- Is life-threatening - this refers to an event in which the subject was at risk of death at the time of the event
- Requires in-subject hospitalisation or prolongation of existing hospitalisation
- Results in persistent or significant disability or incapacity

CONFIDENTIAL

- Is a congenital anomaly or birth defect
- Is judged medical important (this refers to an event that may not be immediately life-threatening or result in death or hospitalisation, but may jeopardise the subject or may require intervention to prevent one of the other outcomes listed above)

11.3 Assessments of AEs and SAEs

Assessment:

When assessing AEs and SAEs the investigator will refer to the product resumes 4.8.

Severity:

The severity of an AE/SAE is a clinical observation assessed by the investigator using the following definitions:

- Mild: Transient symptoms, no interference with the subject's daily activities
- Moderate: Marked symptoms, moderate interference with the subject's daily activities
- Severe: Considerable interference with the subject's daily activities, unacceptable

Potential AEs/SAEs will be treated according to standard practice and if relevant follow-ups will be scheduled with relevant specialist.

Causality / Causal Relationship to IMP:

The following terms and definitions are used when assessing the relationship between an AE/SAE and the relevant trial product (IMP):

- Probable: good reason for sufficient documentation to assume a causal relationship
- Possible: a causal relationship is conceivable and cannot be dismissed
- Unlikely: the event is most likely related to aetiology other than the trial product

Final outcome:

The outcome of an AE/SAE is assessed by the sponsor using the following definitions:

- Recovered/resolved: Fully recovered or has returned to baseline
- Recovered with sequelae: As a result of the AE the subject suffered persistent and significant disability/incapacity
- Not recovered: The condition has not returned to baseline, however symptoms may have improved
- Fatal: Event that results in death – An AE with fatal outcome must be reported as an SAE
- Unknown: The outcome is unknown. This term should only be used when no other definition is possible e.g. the subject is lost to follow-up

11.4 Reporting

SAE reporting will be performed in the e-CRF and reviewed by **the sponsor**. In case of IT breakdown, printed versions of the SAE form will be available at all study sites.

Both the sponsor and the primary investigator must be notified via e-mail or phone within 24 hours:

Sponsor:	[name]
Email address:	[contact]
Primary investigator:	[name]
Email address:	[contact]
Emergency phone:	Not yet available

Serious Adverse Events:

CONFIDENTIAL

SAEs must be reported to the above-mentioned persons immediately (within 24 hours of awareness). Any follow-up data must be detailed in a subsequent SAE form in due time.

The initial SAE report must contain as much information as possible including relevant information from the e-CRF (e.g. medical history, concomitant medication) and must be provided via the e-CRF system. If the reporter does not have access to the e-CRF, e-mail may be used.

The SAE report will remain open as long as new relevant data on the event may emerge. The report will be finalised when all relevant information is collected.

Suspected unexpected serious adverse reaction (SUSAR):

An unexpected serious adverse reaction where source or severity is not consistent with information in the current Summary of Product Characteristics (SmPC).

It is the responsibility of the Sponsor to determine whether a reported SAE is a SAR and whether a SAR is a SUSAR. A SUSAR resulting in death or life threatening must be reported within 7 days after the Sponsor becomes aware of the reaction. Within 8 days after reporting, the sponsor must notify the Danish Health and Medicines Authority and the Committee System on Biomedical Research Ethics of all relevant information concerning follow-up of the reaction. Any other SUSAR must be reported to the above-mentioned agencies within 15 days after the Sponsor becomes aware the reaction. SUSARs must also be reported to all local investigators on all study sites.

11.5 Annual reporting

The Sponsor is responsible for annually reporting SARs and SUSARs to the Danish Health and Medicines Authority and the Committee System on Biomedical Research Ethics and all local investigators on the involved study sites.

12. Data handling / Data Management

Data will be handled according to the law on handling personal data(personodataforordningen). The trial has been reported to 'Datatilsynet' in Region Hovedstaden and approval has been granted (VD-2018-144, I-suite: 6385). The trial will be reported to all involved regions ahead of initiating the trial in each region. Data will be stored for 10 years, after which they will be transferred to "Dansk Data Arkiv" or deleted or anonymised.

12.1 CRF

An electronic CRF (REDCap) is provided and all data related to the trial will be recorded here and provide the basis for a central database.

Data on ultrasound scan and birth outcome may be collected from the subject's medical journal and registered in the e-CRF. The new-born's medical journal will be assessed and possible data on congenital malformations and hospitalization during the first month will be registered in the e-CRF.

The e-CRF is to be completed by the investigator or a delegate at the time of the subject's visit to the clinic so that it always reflects the latest observations on the subject.

At the subject's final visit, the e-CRF should be verified and signed off by the responsible investigator or delegate at the site.

12.2 Laboratory Data

Values from blood and urine samples and ECG will obtained from the medical journal and be entered manually into the e-CRF.

CONFIDENTIAL

13. Statistical evaluation

The primary analysis will consist of a linear mixed effects model taking the full longitudinal design into account. The model will be adjusted for site (categorical variable) due to the stratified design. Subjects will be included in the analysis irrespectively of their adherence to the protocol. The treatment effect for the primary outcome will be presented as the average difference between the mirtazapine and placebo groups in changes in PUQE-24 score from baseline to Day 2 and from baseline to Day 14. These comparisons will be based on the standard errors from the linear mixed model. Sensitivity analyses will be performed using multiple imputation where the imputation model will include all available baseline variables.

Before the randomisation code will be added to the cleaned dataset, a prespecified statistical analysis plan (SAP) will be elaborated and accepted by the statistician and investigators.

All data will be described including data-incompleteness as well as reasons for data-incompleteness. Data will be analysed blinded by the statistician. Any changes to the statistical analysis plan will be described in any future publications.

For further information on the final analysis refer to the SAP.

14. End of trial

Within 90 days after the trial completion the sponsor must inform the Danish Health Authorities and Ethics Committee about the completion. The result of the trial must be submitted within 12 months.

14.1 Early termination of the trial

The sponsor reserves the right to terminate the trial under the following conditions:

- Safety concerns
- If an interim statistical analysis shows that the trial has no scientific value or too low power

If the trial is prematurely terminated or suspended, the investigator should promptly inform the subjects and ensure appropriate therapy and follow-up. Furthermore, the investigator and/or Sponsor should promptly inform the pertinent ethics committee and regulatory authorities.

14.2 Subject Discontinuation

The subject will be advised in the informed consent form that he/she has the right to withdraw from the trial at any time without prejudice. Where discontinuation from the trial is initiated by the subject, the investigator is to ascertain the primary reason for discontinuation from the list below:

- An AE for which the investigator did not consider discontinuation from the trial necessary
- Co-existing disease
- Withdrawal of consent
- Other reasons including treatment failure

The subject may at any time be discontinued from the trial at the discretion of the investigator.

Subjects must be discontinued from the trial under the following circumstances:

- If a criterion equivalent to an exclusion criterion occurs
- If, in the investigator's opinion, continuation in the trial would be detrimental to the subject's well-being
- Occurrence of intolerable AE(s) as determined by the investigator and/or subject
- Subject lost to follow-up
- If the randomisation code is broken
- If informed consent is withdrawn

In all cases, the primary reason for discontinuation must be recorded in the e-CRF and in the subject's medical records. Follow-up on the subject is necessary to establish whether the reason was an AE. If so, this must be reported in accordance with the appropriate procedures.

CONFIDENTIAL

As far as possible, all examinations scheduled for the final visit must be performed on subjects who receive the IMP but do not complete the trial according to the protocol.
 Data obtained until discontinuation will be entered in the clinical database and used for statistical analyses.

15. Administrative procedures

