7.2 Exclusion criteria

- Molar pregnancy, multiple gestation or non-vital pregnancy
- Nausea and vomiting of other aetiology than NVP

CONFIDENTIAL

- Allergic to selective 5-HT3-receptor antagonists
- Ongoing treatment with antidepressant medication
- Pre-existing diagnosis of chronic kidney disease, diabetes type 1 or 2, significant cardiac disease (incl. long QT syndrome), epilepsy, HIV. In case of other pre-existing conditions subjects might be excluded based on individual assessment by an MD
- Elevated liver enzymes (ALAT/ASAT >150 U/l)
- Elevated creatinine (>100 µmol/l)
- ECG showing long QT-syndrome (QTc >460msek)
- Weekly alcohol intake >2 units of alcohol
- Not able to take medicine orally
- Not able to understand spoken and/or written Danish
- Participation in another investigational drug trial within current pregnancy

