7.4 Discontinuation

Subjects will be informed about the possibility of discontinuing the trial at any time. We will encourage the subjects to inform the investigator as soon as they have decided to discontinue the trial and last administration of trial medication will be registered. In case of discontinuation we will ask the subject to indicate a reason for the discontinuation which will be registered. If the reason for discontinuation is treatment failure, time of treatment failure will be registered.

Subjects will be discontinued from the trial in case of icterus or mania or if they comply with an exclusion criterion.

Subjects may be unblinded at discontinuation if this is necessary to make clinical decisions about their future treatment. Subjects will be encouraged to fill out daily online questionnaires on possible side effects until three days after last administration of trial medication.

Birth outcome will be registered on all subjects including dropouts unless subjects withdraw consent.

Data on treatment effect (NVP symptoms) collected before discontinuation will be evaluated and dropouts will not be replaced by new subjects.

All discontinued subjects will have to return the trial medication.

8. Randomisation, treatment blinding / unblinding and sample size

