8.3 Sample Size

The trial is dimensioned to find a difference of 2 in PUQE-24 score change from baseline to Day 2 (short term) and/or from baseline to Day 14(+/-1)(long term) between the mirtazapine group and the placebo group with 80% power based on a standard deviation (SD) of change of PUQE-24 score of 3, a type 1 error rate of 2,5% and 25% drop-out. The reason for the 2,5% type 1 error rate is that we want to test 2 hypotheses; effect of mirtazapine versus placebo short and long term on HG.

Thus, we will have to include 57 subjects in each of the 3 groups, which we round up to 60 subjects, equivalent of 180 subjects all together.

An SD of 3 is a conservative estimate based on the placebo-controlled trial with doxylamine-pyridoxine(39).

9. Trial Products

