6.5 Framework

Two-sided equality test with the null hypothesis is that the expected difference of the effects of mirtazapine and placebo is zero.

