7.4 Analysis populations

The primary analyses will be performed on all subjects randomized in the trial (intention to treat). Sensitivity analyses will be performed on the per protocol population.

8. Trial Population

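### A Day 14 PUQE-24 score from discontinued women is neither clearly required nor clearly analysed, so the all-randomised Day 14 result rests on an unstated missing-at-random assumption

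*Protocol*

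**What the plan says.** **After discontinuation.** Protocol 7.4 states "Subjects will be encouraged to fill out daily online questionnaires on possible side effects until three days after last administration of trial medication", and adds that birth outcome is registered. On efficacy it says "Data on treatment effect (NVP symptoms) collected before discontinuation will be evaluated". Protocol 8.2 requires discontinuation after any code break and lists side effects, adverse events and birth outcome as what is still collected. SAP 6.3 lists birth outcome only.

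**The end of Protocol 14.2.** Two adjacent sentences matter. The first asks that the final-visit examinations be done, so far as feasible, in treated women who do not complete. Protocol 10.1 includes PUQE-24 at Visit 3. The second reads "Data obtained until discontinuation will be entered in the clinical database and used for statistical analyses".

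**Who is discontinued.** Protocol 14.2 makes discontinuation mandatory "If a criterion equivalent to an exclusion criterion occurs", and Protocol 7.4 says the same. One exclusion criterion in Protocol 7.2 is "Not able to take medicine orally". Criteria are re-assessed at Visits 2 and 3. Protocol 10.17 defines treatment failure as a decision to leave the trial because of insufficient relief.

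**The analysis.** SAP 7.4 puts the primary analyses on all randomised women, by intention to treat. Protocol 13 and SAP 9.2 use a longitudinal mixed model and include women regardless of adherence. SAP 9.3 leaves missing data to that model, checked by multiple imputation. For the imputation model, SAP 9.2 names only baseline variables.

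**The concern.** The plan promises a Day 14 comparison of everyone randomised, but does not define a status of having stopped trial medication while still being followed for PUQE-24. The reasons for leaving are tied to the outcome. Protocol 6.2 itself observes that women scoring 13 or more often cannot keep tablets down, so severe symptoms can lead to a mandatory exit. Poor relief leads to a voluntary one.

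Missing Day 14 scores are then unlikely to be a random subset, and their share may differ by arm. The mixed model replaces them with what the earlier recorded scores predict. That equals the all-randomised effect only under missing at random, which neither document states or tests. No missing-not-at-random analysis is planned. Scores that were never collected cannot be recovered later.

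**Working it through.** **1. Reading the two sentences in Protocol 14.2.** There are three ways to take them together.
- The final-visit examinations are done on the day of exit. A woman leaving on Day 5, say, then gives a Day 5 score, not a Day 14 score.
- They are done on Day 14. The score then postdates discontinuation, and the next sentence, which covers data up to discontinuation, does not say that it is used.
- They are done on Day 14 and analysed. Nothing in the SAP says so.

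The text does not choose between these. The provision also covers only women who received trial medication.

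**2. The plan's sample size.** Inputs: difference 2, SD 3 and 80% power (Protocol 8.3); "a type 1 error rate of 2,5% and 25% drop-out" (same section); two-sided testing (SAP 6.5, "Two-sided equality test with the null hypothesis").

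n = 2 × [SD × (z₀.₉₈₇₅ + z₀.₈₀) / difference]² = 2 × [3 × (2.241 + 0.842) / 2]² = 42.77 per arm.

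42.77 / 0.75 = 57.03, which matches the stated 57, rounded up by the plan to 60.

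Expected loss is 0.25 × 60 = 15 per arm, leaving 45. Power for a difference of 2 is then 82% by the normal formula (81% by the t-test). With all 60 observed, and the same difference and SD, it is 92% (91%). The 25% allowance therefore protects precision as intended. It does nothing about bias.

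**3. Size of a possible bias.** Change is baseline minus Day 14, so larger is better. Let p be the proportion leaving in an arm, and δ the number of points by which those women's true Day 14 scores are worse than the model predicts. The arm's all-randomised mean change is the model's mean minus p × δ. For mirtazapine minus placebo:

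all-randomised effect = model effect + δ(placebo) × p(placebo) − δ(mirtazapine) × p(mirtazapine).

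With the same δ in both arms, the shift is δ × [p(placebo) − p(mirtazapine)]. The documents give 25% overall and no split by arm, so every split and every δ below is an assumption. The model estimate is set at 2.0.

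| Drop-out, placebo / mirtazapine | Departure δ | All-randomised effect |
|---|---|---|
| 25% / 25% | 1–3, both arms | 2.0 |
| 30% / 20% | 1–3, both arms | 2.1–2.3 |
| 35% / 15% | 1–3, both arms | 2.2–2.6 |
| 20% / 30% | 1–3, both arms | 1.9–1.7 |
| 15% / 35% | 1–3, both arms | 1.8–1.4 |
| 25% / 25% | 1–3, mirtazapine only | 1.75–1.25 |

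With equal departures the shift is 0.1–0.3 for a 10-point difference in drop-out (1–3 × 0.10) and 0.2–0.6 for a 20-point difference (1–3 × 0.20). That is 5–30% of the design difference. If women who leave do better than predicted, the signs reverse.

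**4. When the mixed model is and is not enough.** This is an illustrative simulation with 6,000 per arm, daily scores, an assumed true on-treatment effect of 2 and symptom-driven drop-out of 27–30% on placebo and 14–17% on mirtazapine.

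| Drop-out depends on | Worsening after leaving | All-randomised effect | Mixed model |
|---|---|---|---|
| last recorded score | none | 2.03 | 2.04 |
| last recorded score | 1–3 points | 2.17–2.31 | 2.02–1.96 |
| the unrecorded score | none | 1.97 | 1.88 |
| the unrecorded score | 1–3 points | 2.12–2.31 | 1.90–1.83 |

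In the first row the mixed model recovers the all-randomised effect, while completers alone give 1.89. A gap appears when exit depends on a score that was not recorded, or when the course changes after leaving. In this set-up, where placebo loses more women, the model understates the effect.

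**The case against.** The strongest defence is that the plan already handles this. The final-visit provision in 14.2 may well yield a PUQE-24 score. Neither 7.4 nor 14.2 says that only data before discontinuation will be used, so both sentences can be read as a promise to keep the data of women who leave. Daily scores up to exit stay in the model and inform Day 14. SAP 8.4 lists discontinuation, glossed as stopping the intervention, separately from loss to follow-up. A woman who takes few capsules but stays in the trial is still followed and analysed. Severe vomiting is not automatically an exit, since Protocol 9.1 provides for re-dosing and 9.5 for intravenous rescue. Code breaks for continued treatment come at Visit 3 and need not cost a Day 14 score. Protocol 6.2 foresaw drop-out and answered with the Day 2 co-primary and the treatment-failure endpoint.

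Much of this stands, and it rules out stronger readings. A reader might infer that PUQE-24 follow-up simply ends at discontinuation; the final-visit sentence prevents that. A reader might infer that the Day 14 endpoint loses the worst outcomes and is not an intention-to-treat result; that is conditional, as the first simulated case shows. A reader might infer that the trial is underpowered; it is not, because 80% power after 25% drop-out was planned.

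What remains is that the two sentences in 14.2 are unreconciled and that the missing-at-random assumption is neither stated nor tested. The Day 2 endpoint does not repair the Day 14 one.

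A further objection is that scores after stopping may be unblinded, and may reflect other treatment: Protocol 3.3 names ondansetron as the likely alternative outside the trial. That is a real cost, which the fix has to handle openly.

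**Conclusion.** The point holds as a gap in the protocol text with a conditional statistical consequence. **Should-fix.** The textual part needs no assumption: no section clearly requires a Day 14 PUQE-24 score from a discontinued woman, and none clearly says that such a score would be analysed.

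The planned Day 14 analysis estimates the all-randomised effect if women who leave follow the course that their recorded scores predict. If they do not, the documents fix neither the size nor the direction of the bias. The range of 0.1–0.6 points rests on assumed 10–20 percentage-point differences in drop-out and equal 1–3 point departures; it is zero if both are equal across arms. Departures confined to one arm could give other values, as the table shows.

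A reader might infer that the planned analysis flatters mirtazapine. The documents do not support that. If placebo loses more women and they do worse than predicted, the planned estimate is conservative; if mirtazapine does, it is optimistic.

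**What to change.** In Protocol 7.4, 8.2 and 14.2, state that women who stop trial medication for any reason are asked to keep completing the existing online PUQE-24 form to Day 14, unless they withdraw consent to data collection. Reconcile the last two sentences of 14.2 so that these scores are entered and used in the primary all-randomised analysis, and say the same in SAP 9.2. Flag each record as on or off treatment and as blinded or unblinded. Give an analysis restricted to on-treatment, blinded data as a sensitivity analysis.

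The cost is a short amendment to the protocol and consent wording. The form is already online, and discontinued women are already asked for side-effect questionnaires, so no new instrument or visit is needed. The downsides are extra questionnaire burden for women who have stopped, and the inclusion of some off-treatment or unblinded self-reported scores, which could move the contrast in either direction. No rule on when treatment stops is changed.
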